15.7 Safety measurements

15.7.1 Specific safety measurements

Due to the short treatment duration, the topical administration (associated with a low risk of systemic availability of pyrethrum) and comprehensive data on the safety profile of the active substance, special safety investigations (e.g. laboratory safety tests) will not be performed routinely.

No further special safety investigations will be carried out during the study as sufficient information about the investigational products is already available.

15.7.2 Checks for general well-being

The observation phase for PTSS will start one week prior to the first intended study drug administration, for AE's with signing the informed consent, and will end with the release of the subject from the study examination.

Checks for general well-being will be performed in a non-leading manner. In addition to the checks for general well-being at the first visit (0h, 1h p.a.), checks will also be performed, on study day 1 as well as on study day 7 (0h, 1h p.a.) and at the final visit on study day 10.

A registered physician will be available throughout the entire study and all patients will be observed for signs of clinical toxicity during the entire study.

15.7.3 Pre-treatment signs and symptoms and Adverse Events

15.7.3.1 Definition of pre-treatment signs and symptoms and Adverse Events

A **pre-treatment sign and symptom (PTSS)** is defined as any acute existing disease or symptom, which occurs during one week prior to the first intended study drug administration. If, after administration of the investigational product, a deterioration of the intensity of the pre-treatment sign or symptom is observed, this sign and symptom will be documented as an Adverse Event.

An **Adverse Event (AE)** is any unintended or unfavourable sign (including an abnormal finding), symptom or disease occurring in a subject after signing the informed consent until the last study visit, whether or not the event is believed to be causally related to study medication (IMP) or comparative compound. This definition includes any worsening of conditions that were present at the time of entry into the study (signing of the informed consent) (see International Conference on Harmonization (ICH-E2A). AEs occurring after signing the informed consent but before administration of study medication are defined as non-treatment-emergent events. Those events are evaluated separately because in these cases a causal relationship with the study medication can be excluded.

Adverse Drug Reaction: In the pre-approval clinical experience with a new medicinal product or its new usages, particularly as the therapeutic dose(s) may not be established: all noxious and unintended responses to a medicinal product related to any dose should be considered Adverse Drug Reactions. The phrase "responses to a medicinal product" means that a causal relationship between a medicinal product and an Adverse Event is at least a reasonable possibility, i.e., the relationship cannot be ruled out. Regarding marketed medicinal products: a response to a drug which is noxious and unintended and which occurs at doses normally used in man for prophylaxis, diagnosis, or therapy of disease or for modification of physiological function (see the ICH Guideline for Clinical Safety Data Management: Definitions and Standards for Expedited Reporting).

Unexpected Adverse Drug Reaction: An Adverse Drug Reaction, the nature or severity of which is not consistent with the applicable product information e.g. Investigator's Brochure for an unapproved investigational product or package insert/summary of product characteristics for an unapproved product or package insert/summary of product characteristics for an approved product (see: ICH Guideline for Clinical Safety Data Management: Definitions and Standards for Expedited Reporting).

A Serious Adverse Event (SAE) / Serious Adverse Drug Reaction (Serious ADR) is defined as any untoward medical occurrence that at any dose

- results in death, or
- is life-threatening, or
- requires inpatient hospitalisation or prolongation of existing hospitalisation, or
- results in persistent or significant disability/incapacity, or
- results in a congenital anomaly/birth defect.

Important medical reactions that may not be immediately life-threatening or result in death or hospitalisation but may jeopardise the patient or may require intervention to prevent one of the other outcomes listed in the definition above should also be considered serious.

Examples of such events are intensive treatment in an emergency unit or at home for allergic bronchospasm, blood dyscrasia or convulsions that do not result in hospitalisation, or development of drug dependency or drug abuse.

The term "life threatening" in the definition refers to an event in which the patient was at risk of death at the time of the event; it does not refer to an event, which hypothetically might have caused death if it were more severe.

Hospital admission is usually interpreted as requiring at least one overnight stay. A requirement for out-patient treatment in an emergency room is not, by itself, an SAE although the event requiring treatment may be. Elective surgery or other elective procedures which require hospitalisation are not SAEs if the condition being treated or investigated was preexisting at the time of entry into the study and did not worsen during the study. However, any untoward outcome of any such procedure should be reported as a non-serious AE or an SAE, as appropriate.

Persistent or significant disability or incapacity means that symptoms which disable the subject, defined as a substantial disruption in a person's ability to conduct normal life functions, do not resolve when study drug is discontinued.

To ensure that there is no confusion or misunderstanding of the difference between the terms "serious" and "severe", which are not synonymous, the following should be considered: The term "severe" is often used to describe the intensity (severity) of a specific event (as in mild, moderate, or severe myocardial infarction); the event itself, however, may be of relatively minor medical significance (such as severe headache). This is not the same as "serious", which is based on subject / event outcome or action criteria usually associated with events that pose a threat to a subject's life or functioning. Seriousness (not severity) serves as a guide for defining regulatory reporting obligations.

Scientific and medical judgment should be used when deciding whether an event is serious.

However, in situations where there is any uncertainty or ambiguity, the event should be managed and reported as if it were serious.

Suspected Unexpected Adverse Drug Reaction – SUSAR is an unexpected Serious Adverse Event causally at least possibly related to the investigational product. If a SAE will be classified as a SUSAR will be decided by sponsor's drug safety department.

15.7.3.2 AE-Assessment

Each AE will be assessed by an investigator according to the following categories:

Category	Characteristics	Explanations
Serious	Non serious	
	Serious	Results in death
		Life threatening
		Persistent or significant disability / incapacity
		 Hospitalisation/Prolongation of existing hospitalization
		Congenital anomaly/birth defect
Expected	Not applicable	There is no causal relationship to investigational product assumed.
	No	 Nature, severity, intensity or outcome of the adverse reaction is not consistent with SPC/Investigator's Brochure.
	Yes	 Nature, severity, intensity or outcome of the adverse reaction is consistent with SPC/Investigator's Brochure.
Intensity	Mild	 Patient perceives signs or symptoms, but is easily able to tolerate those, his activity is not reduced.
	Moderate	 Signs and symptoms limit patient's normal activities, but don't stop them.
	Severe	Patient is not able to pursue his normal activities.
Causal	No relation	Components of assessments of causal relationship
relationship to investigational product		 Exposition: Was the investigational product really applied?
	Possible relationship	• Time course: Was the administration of the investigational product followed by the AE in a reasonable time interval?
	Probable relationship Certain relationship	 Probability: Are there other possible reasons for the AE, e.g. concomitant diseases, concomitant medication, environmental or
		individual factors?
		 Was the AE terminated or improved after reduction or the stop of medication?
		 Did the AE reoccur or worsen after reapplication of study drug?
Action taken regarding study drug	None	No change of the planned further application.

Category	Characteristics	Explanations
	Interrupted	Application was interrupted for a short time.
	Disrupted	Application was terminated.
	Increased	Dose was increased.
	Reduced	Dose was reduced.
	Unknown	There are no details known.
	Not applicable	Change of dose was not possible, because for instance application was terminated.
Outcome	Recovered/resolved	The AE is completely subsided. There are no effects felt. Previous status is restored.
	Recovered with sequelae	The AE is subsided, but patient suffers from symptoms, for instance persistent cough.
	Recovering	The AE is improved, but patient still feels effects. Recovery is foreseeable.
	Ongoing	 The AE is not resolved, symptoms persist unchanged.
	Fatal	Patient dies due to the AE.
	Follow-up impossible	 Outcome is unknown because patient didn't come to the follow-up visit. Efforts to get follow-up information failed.

For PTSS only the assessment of intensity will be performed in the same way as for AE.

15.7.3.3 Documentation and Reporting

Documentation of AE or PTSS

Any PTSS or AE, reported spontaneously by a volunteer or observed by the study personnel has to be documented in the CRF regardless if causally related to the investigational product or not.

The event will be described in precise way using common medical terminology. Abbreviations have to be avoided. If possible a diagnosis should made otherwise symptoms will be documented.

The following characteristics of a PTSS have to be documented:

- Description of PTSS
- time of onset and stop time
- severity
- action taken regarding subject
- change to an AE by deterioration

The following characteristics of an AE have to be documented:

- Description of AE
- Time of onset and stop time
- Seriousness
- Expectedness
- Relationship to study drug
- Action taken regarding study drug
- Action taken regarding subject
- Outcome

Reporting of SAE (Serious Adverse Event)

All SAE causally related to study drug or not have to be documented using an additional SAE reporting form. The investigator has to fax SAE report forms within 24 hours after receiving information about the occurrence of an SAE or changed information about a previously reported SAE to sponsor's drug safety.

Drug safety [name] Fax: [name]

If the SAE results in death the investigator is obliged to provide further information on request of the ethics committee, the authorities or the sponsor.

An event only classified as a SAE due to hospitalization starts at that time, when the patient arrives at hospital.

The initial SAE report should contain all available information at least:

- Study code
- Patient number
- Date of first dose
- Date of last dose
- Start time
- Description of SAE (diagnosis, symptoms)
- Individual patient data like age, gender
- Concomitant therapy
- Assessment of causality
- Name of investigator

Any effort has to be made to get further information. If new information is received a Follow-up SAE reporting form has to be sent within 24 hours to the drug safety. The case report may be seen as complete if sufficient information regarding causal relationship and outcome is available and no further information is to be expected.

Follow-up of subjects after Adverse Events

The study staff of the clinical facility has to monitor the trial subject's safety from the occurrence of an AE until recovery, return to baseline or a stable state will be achieved. In single cases

follow up of an AE/SAE after last visit can be omitted if there is no causal relationship to study drug and patient's state is improved or stabilised.

Sponsor's responsibility

The sponsor should expedite the reporting to all concerned investigator(s) / institution(s) and to the regulatory authority(ies) of all AE's that are both serious and related. Such expedited reports should comply with the applicable regulatory requirement(s) and with the ICH Guideline for Clinical Safety Data Management: Definitions and Standards for Expedited Reporting.

15.8 Prior and concomitant therapy

Topical use of medication on scalp and hair, prior to the first intended administration of the investigational products, which is listed in the exclusion criteria (see section 14.2), will prevent inclusion into the study.

Treatment of a previous anti-lice treatment with exception of combing the hair using a lice comb within 30 days will prevent inclusion into the study. Treatment with an anti-lice treatment during the study will lead to exclusion of the patient.

Any pre-existing chronic medication taken for treatment of existing disorders and not considered to interfere with the study course or to influence scalp healing will be allowed.

Intake of pre-existing chronic medication used by the patient should be continued throughout the study at a conventional dose and schedule. Their use is to be recorded in the CRF and medical records.

Checks for concomitant medication will be performed at all study visits.

If a patient needs concomitant medication during the study, the responsible investigator should be asked. Concomitant medication is to be documented by brand, type (generic name, if applicable), amount and duration on the CRF. The Principal Investigator / investigator will then decide together with the responsible project manager of CardioSec Clinical Research GmbH, whether the patient has to be excluded.

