14.5 Removal of volunteers from treatment or assessment

Withdrawal criteria

- Serious Adverse Events (SAE's)
- Diseases requiring treatment that occur during the study, which do not constitute SAE's but which, in the opinion of the Principal Investigator, would probably prevent achievement of the study objectives.
- Non-adherence to the study conditions or relevant deviations from procedures as established in the study protocol.
- Withdrawal of consent.
- Duration of treatment < 10 minutes for **GOLDGEIST[®]** FORTE.
- Severe irritation of the skin or the eyes on pre-treatment assessment on day 7
- Use of any other anti-head lice therapy.

All details and reasons for removal of trial subjects from the study will be recorded in the study termination section of the CRF. CRFs of all trial subjects entered into the study have to be kept in the documentation of the study. Reasons for withdrawal of trial subjects will be entered into the final report of the study. Every effort has to be made to follow-up trial subjects who terminate with drug-related AE's in order to determine the final outcome.

Follow-up of withdrawn patients, drop outs

A drop out is a patient, who prematurely discontinues participation after being enrolled. If a patient drops out, possible PTSS (Pre-treatment Sign and Symptom) or AE's will be recorded as long as necessary. A post-study examination should be performed if possible.

All PTSS/AE's documented during the study for the drop out will be considered in the assessment. Other data recorded for the drop out are contained in the individual patient listing in an appendix to the study report.

Replacements

Patients who prematurely discontinue participation will be replaced.

Removal of volunteers from assessment

Screening failures

Screening failures are volunteers who were screened but not enrolled.

Screening failures including reason will be listed in the screening list. All data obtained within the screening will be documented in the patient's record. In case that entries were made to a CRF it will be archived, but not entered in the database.

Screening failures will not be listed, as no CRF data is included in the database.

Safety set

The safety set/population consists of all patients who were randomised and exposed to study medication.

Per-protocol set

All subjects

- without any major protocol violation
- with available values of the relevant study variables

will be included in the per-protocol-set/population.

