15.2.4 Follow-up Visit V04 (day 10)

The final visit will be performed on study day 10 (-1; +2 days).

The final visit examination is performed in order to verify if the patient is cured. A patient will be considered cured, if no living head lice could be detected. If living lice present on day 10, the life stages of the lice will be documented. If any other pediculocidal agents employed during the observation period, the patient will be considered a treatment failure.

The following examinations will be performed within the final visit:

- Hair scalp assessment for living lice (all stages) by study staff
- Assessments of skin and eyes irritation, global tolerability, local tolerability
- Questioning on well-being
- Questioning on patient's combing
- Registration and documentation of any adverse events and/or changes regarding concomitant diseases, concomitant medication, withdrawal criteria

In case that the examination (diagnostic combing) will show active head lice infestation (living nymph or imago), the patient will be considered treatment failure or re-infestation and will be referred to a specialist for further treatment.

Subjects exhibiting either subjective or objective abnormalities when the trial has been completed will be followed up. Any AE which remains unresolved after completion of the trial requires detailed evaluation and follow-up until the AE has been resolved or a reasonable

explanation for its persistence is found. If the subject refuses to follow the instructions of the study staff, the latter is released from responsibility.

At the final visit each trial subject participating in this study will be advised not to participate in any clinical drug studies for a minimum period of two months following this study.

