16.3 Analysis of primary objective

The cure rate p is defined as proportion of patients who will be found to be cured at evaluation follow-up-visit V04 among all patients received any treatment at visit V01.

The aim of the study is to show superiority for the cure rate of investigated treatment p_T versus a predefined limit of 70%. This limit refers to cure rates found for several formulations which are accepted for the intended use.

The following null hypothesis will be tested:

 $H_{0,prim}$: $p_T = 70\%$

If $p_T > 70\%$ and the null hypothesis is rejected by a two sided, one sample χ^2 -test at 0.05 level, superiority will be concluded.

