16.8 Quality control for statistical procedures

The statistical analysis will be conducted in compliance with the ICH E9 Note for Guidance on Statistical Principles for Clinical Trials (CPMP/ICH/363/96, 1998).

Quality control will be performed according to the SOPs of ACOMED statistik. Quality control includes checks of data, checks of calculations as well as formal checks of tables, listings and figures. All steps of quality control will be documented with signature of the reviewer and date of review.

17 Evaluation of efficacy parameters

The ITT population will be used for analysis of efficacy variables with exception of noninferiority, where PP population will be investigated.

The primary analysis will be repeated for PP population.

Missing values will not be imputed patients dropping out because of non-effective treatment will be counted as non-responders by study design.

Details of the analysis will be fixed in the Statistical Analysis Plan (SAP) which will be finalised before database lock.

18 Evaluation of safety parameter

For definition of safety set/population see section 16.1.

All analyses will be performed for the safety population. Due to the short treatment duration, the topical administration (associated with a low risk of systemic availability of pyrethrum or mineral oil) and comprehensive data on the safety profile of the active substance, laboratory safety tests will not be performed routinely.

Secondary parameters for tolerability and safety:

Local tolerability assessment (subjective	Burning, paraesthesia, pruritus at day 0 (0h, 1h), day 1, day 7 (0h, 1h) and day 10 p.a.
symptoms)	Frequencies and percentages (related to number of patients with information) will be given for each symptom.
Global tolerability	Patients will assess the overall treatment tolerability at day 10 p.a.
assessment (patient):	Frequencies and percentages (related to number of patients with

	information) will be given for each score as well as for the combined score "very good" / "good".
Global tolerability assessment (study staff):	The investigator will assess the overall treatment tolerability at day 10 p.a.
	Frequencies and percentages (related to number of patients with information) will be given for each score as well as for the combined score "very good" / "good".
Skin irritation	Secondary infection, erythema, excoriation of the skin at -1h (baseline assessment), day 0 (0h, 1h), day 1, day 7 (pre-treatment, 0h, 1h) and day 10 p.a.

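### Use of another lice product is a treatment failure in section 15.2.4 but leads to withdrawal, replacement and exclusion in 14.5 and 15.8, and no analysis rule settles whether the patient stays in the cure rate tested against 70%

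*Protocol*

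**What the plan says.** Three sections give consequences for the same event.

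- **Section 15.2.4** gives an outcome: "If any other pediculocidal agents employed during the observation period, the patient will be considered a treatment failure".
- **Section 14.5** lists it among the withdrawal criteria: "Use of any other anti-head lice therapy". On replacement it says: "Patients who prematurely discontinue participation will be replaced". For a drop-out, adverse events and pre-treatment signs enter the assessment, and then: "Other data recorded for the drop out are contained in the individual patient listing in an appendix to the study report".
- **Section 15.8** states: "Treatment with an anti-lice treatment during the study will lead to exclusion of the patient". It does not say whether this means exclusion from treatment, from the study or from the analysis.

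The analysis sections do not name the event. Section 16.3 takes the cured at V04 "among all patients received any treatment at visit V01". Section 17 says: "The ITT population will be used for analysis of efficacy variables with exception of noninferiority, where PP population will be investigated". Section 17 also rules out imputation and adds that "patients dropping out because of non-effective treatment will be counted as non-responders by study design". Sections 16.1 and 14.5 define a safety set and a per-protocol set, but no ITT set.

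**The concern.** By 15.2.4 every user of another product is a failure. Under 14.5 the same patient may be withdrawn before V04, be replaced, and have efficacy data that appear only in a listing. If the recorded termination reason is the prohibited product and not lack of effect, the non-responder sentence in section 17 does not plainly reach the patient, and nothing is imputed. An analyst could then drop a known failure and cite the protocol for doing so.

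In the primary test the direction of such an error is fixed. The test product's rate is compared with a constant 70%, so removing failures can only raise it, and no second arm offsets the effect. The reference product, tested in the same way, would benefit likewise. In the two-arm superiority test the direction would depend on how many users each arm had.

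**Working it through.** **1. The passages side by side**

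- Pointing to not cured and in the denominator: 15.2.4 (failure), 16.3 (all treated at V01), section 17 (ITT for efficacy).
- Pointing to removal: 14.5 (withdrawn, replaced, efficacy data listed only), 15.8 (excluded), section 17 (no imputation; non-response only for drop-out through lack of effect). Section 16.5 also inflates the sample for drop-outs, treating them as cases to be made up.
- Missing link: a definition of ITT, and a statement of which group of passages governs the analysis.

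**2. The plan's own sample size**

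Inputs from 16.5: 90% against 70%, two-sided alpha 0.05, power 90% (or 80%).

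n = [(1.96 × √(0.7×0.3) + z_power × √(0.9×0.1)) / 0.2]² = 41.13, rounded up to 42 (33.10, rounded up to 34, at 80% power). Then 42 × 1.1 × 1.05 = 48.5, so 49, taken as 50 per arm. These figures reproduce and are not in dispute.

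**3. The decision rule with all 50 kept**

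z = (x − 0.7n) / √(n × 0.7 × 0.3), with success if z ≥ 1.96.

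- x = 42, n = 50: z = (42 − 35)/3.240 = 2.160, success.
- x = 41, n = 50: z = (41 − 35)/3.240 = 1.852, no success.

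So 42 of 50 are needed. The exact upper-tail error at a true 70% is 1.8% (nominal 2.5%), and the power at 90% is 94.2%.

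**4. Removing failures from a fixed result**

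| Cured | All kept | Users removed |
|---|---|---|
| 41 | 41/50 = 82.0%, p = 0.064 | one removed: 41/49 = 83.7%, z = (41 − 34.3)/3.208 = 2.089, p = 0.037 |
| 40 | 40/50 = 80.0%, p = 0.123 | two removed: 40/48 = 83.3%, z = (40 − 33.6)/3.175 = 2.016, p = 0.044 |

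**5. Error rate at a true cure rate of 70%**

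The protocol gives no share of users. Assume that a share g of failures uses another product. The share of treated patients is then f = 0.30g, and the cure rate among those left is 0.70/(1 − f). The number removed is binomial(50, f), and the critical value is recalculated for each remaining n.

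| g (assumed) | f | Expected users among 50 | Upper-tail error if removed |
|---|---|---|---|
| 0% | 0% | 0 | 1.8% |
| 5% | 1.5% | 0.75 | 3.0% |
| 10% | 3% | 1.5 | 4.4% |
| 20% | 6% | 3 | 8.2% |
| 30% | 9% | 4.5 | 15.3% |

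Replacement changes little. At f = 6%, the error with users removed and replaced so that 50 are analysed is 7.9%, against 8.2% without replacement.

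**The case against.** The best reply is that 16.3, the section on the primary analysis, already gives the right answer. A treated patient withdrawn for using another product is in its denominator and, not having been found cured at V04, is not in its numerator. Withdrawal in 14.5 is a rule on participation, and a patient can be both withdrawn and a failure. Exclusion in 15.8 stands in a section on concomitant therapy and most naturally means exclusion from participation. A family that switches because lice persist might also be covered by the non-responder sentence in section 17. Section 14.5 asks for a post-study examination of drop-outs where possible, so a late reading is not ruled out.

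Much of this stands. A reader might infer that the sections assign opposite outcomes, or that these failures do disappear from the primary test. The documents support neither: only 15.2.4 assigns an outcome, and 16.3 read alone keeps the patient as not cured.

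The reply does not close the gap. The efficacy analysis is assigned to an undefined set. No passage says how a withdrawal for a prohibited product maps to the non-responder rule. The listings-only sentence in 14.5 is not limited to participation. An SAP may add detail, but the conflicting rules are in the protocol, and withdrawal and replacement take place at the site before any analysis.

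The size is also conditional. With 5% of failures switching, the error is 3.0%, close to the nominal 2.5%. The 41/50 example is a borderline result: at the planned 90% cure rate exactly 41 cures occur with probability 3.3%.

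**Conclusion.** The point holds as an unresolved contradiction with a possible consequence. It does not show that failures are lost from the primary test. The protocol supports both keeping and removing a patient who used another lice product; 16.3 and 15.2.4 favour keeping, without settling it. If such patients were removed, the test product's rate against 70% could only rise. One patient could then turn p = 0.064 into p = 0.037, and the upper-tail error at a true 70% would move from 1.8% to 3.0%, 4.4%, 8.2% or 15.3% for 5%, 10%, 20% or 30% of failures switching.

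Those error rates rest on two assumptions: that every user is removed, and the assumed share of users. The single-patient example needs only the first.

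**What to change.** State one analysis rule in 16.3 and section 17, and refer to it from 14.5 and 15.8. In the primary and superiority analyses, every patient treated at V01 with recorded use of another lice product before V04 stays in the denominator and counts as not cured. This applies whatever termination reason is recorded and whether or not the patient is replaced. It is what 15.2.4 and 16.3 already imply.

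Define the ITT set to match the 16.3 denominator. State that exclusion in 15.8 and the listings-only sentence in 14.5 do not remove the patient from this analysis.

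Whether such a patient continues in the study is a clinical matter. Sections 14.5, 15.2.4 and 15.8 must be reconciled on it by the sponsor, and no rule is proposed here.

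The cost is wording only. The flow chart already has concomitant medication and restrictions checked at V02 to V04, so no new data are needed. The cure rate will be slightly less favourable if such patients occur.
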